- a. Using total active minutes per day as measured by multi-directional accelerometry. One week before each study assessment visit, participants will wear Actical Physical Activity MonitorsTM (Philips Respironics, Bend, OR) on their dominant hip during waking hours for a period of 7 days with 15 second epochs. This technique is considered the gold standard for physical activity assessment. ⁶⁰ During any cycling exercise, participants will wear the device on their dominant ankle. Valid files for analysis will require at least 3 days with a minimum of 8 h of wear time per day. Total active minutes will be calculated by summing the minutes per day spent in light intensity and moderate-to-vigorous physical activity (MVPA) based on pre-specified activity count cut points. ^{61, 62} Accelerometry is included to adjust for physical activity in the control group and address potential contamination.
- b. Using the Godin-Shephard Leisure-Time Exercise Questionnaire, which uses frequency and intensity of leisure time activity to calculate a total leisure time activity score. (REF)

The total leisure time activity score has been validated against measures of physical fitness and objective measures of physical level activity collected by accelerometry in individuals with chronic disease. ^{63, 64}

- **4.** Change in Exercise Capacity from baseline to 12, 26 and 52 weeks as measured by Incremental Shuttle Walk Test (ISWT) (Appendix B-3). Total distance is recorded as individuals walk 10-meter lengths to self-reported exhaustion at pre-programmed progressively increasing speeds as indicated by recorded beeps. ISWT has been used repeatedly in elderly and CKD populations, minimal clinically important differences have been established in chronic disease populations and results are correlated with other measures of exercise capacity. 65,66-68 ISWT was chosen to objectively measure physical function because standardized walking speeds at each stage make it less subject to measurement error due to variable participant effort than other similar tests.
- **5.** Change in frailty status from baseline to 12, 26 and 52 weeks assessed using the Modified Fried Criteria. ^{69,70} Defined as the presence of ≥ 3 criteria of the following criteria: weight loss; exhaustion; slowness; low physical activity; and weakness. As a predictor of adverse outcomes and associated with symptom burden, it is important to determine if frailty status can be modified through exercise

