7.2 Study Outcome Evaluations

Outcome assessments (as detailed in Section 4.2) will occur at baseline, 12, 26 and 52 weeks (within +/-10 days of this time point) and be performed pre-dialysis on a midweek dialysis day to minimize the effects of fluid overload and dialysis fatigue, but maximize convenience and adherence to the assessment schedule. In our pilot study, assessment visits took 30 minutes.

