9.3.3 Secondary Outcomes and Analyses

We will repeat the primary outcome analyses that compared change in DSI from baseline to 12 weeks between groups, instead looking at change from baseline to 26 weeks and 52 weeks.

Change in EQVAS over time will be compared between study groups using Student's T-test. As well, we will compare the difference in proportion of individuals who develop new deficits (score of 2 or 3) in each domain of the EQ5D-5L over time. The degree to which change in symptom burden correlates with change in EQVAS will be assessed using Spearman and Pearson's correlation coefficients as indicated based on distribution of the data. Change in all other secondary outcomes over time will be compared between groups using the appropriate parametric and non-parametric statistical tests depending on data type and distribution. Bonferroni adjustments will be made for secondary outcomes to adjust for multiple study timepoints. Hospitalization will be analyzed using Poisson regression. For all analyses, two-sided p < 0.01 will be statistically significant. Statistical analysis will be performed using SAS 9.3 (Carey, NC).

We will validate the Godin Shepard Leisure-Time Exercise Questionnaire using accelerometry data. Correlation between Godin Questionnaire Score and active minutes (light, moderate and moderate-vigorous activity) measured by accelerometry at each study assessment time point will be assessed using Pearson or Spearman correlation depending on distribution of the data. Internal consistency of the Godin questionnaire will be assessed using Cronbach alpha and Intraclass Correlation Coefficient. In those individuals in which active minutes measured using accelerometry did not change between assessment periods (change of less than 10% from baseline), test re-test reliability of the Godin Questionnaire will be assessed using Kappa statistic. Responsiveness will be modelled using linear regression with Godin questionnaire score as the primary predictor of active minutes measured by accelerometry. Additional predictors including sex, age, diabetes and other comorbidities will be added to the model as sample size will allow.

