Appendix 3.3: Godin Leisure-Time Exercise Questionnaire

INSTRUCTIONS

In this excerpt from the Godin Leisure-Time Exercise Questionnaire, the individual is asked to complete a self-explanatory, brief four-item query of usual leisure-time exercise habits.

CALCULATIONS

For the first question, weekly frequencies of strenuous, moderate, and light activities are multiplied by nine, five, and three, respectively. Total weekly leisure activity is calculated in arbitrary units by summing the products of the separate components, as shown in the following formula:

Weekly leisure activity score = $(9 \times \text{Strenuous}) + (5 \times \text{Moderate}) + (3 \times \text{Light})$

The second question is used to calculate the frequency of weekly leisure-time activities pursued "long enough to work up a sweat" (see questionnaire).

EXAMPLE

Strenuous = 3 times/wk

Moderate = 6 times/wk

Light = 14 times/wk

Total leisure activity score = $(9 \times 3) + (5 \times 6) + (3 \times 14) = 27 + 30 + 42 = 99$

Godin Leisure-Time Exercise Questionnaire

1. During a typical **7-Day period** (a week), how many times on the average do you do the following kinds of exercise for **more than 15 minutes** during your free time (write on each line the appropriate number).

a) STRENUOUS EXERCISE (HEART BEATS RAPIDLY)

(e.g., running, jogging, hockey, football, soccer, squash, basketball, cross country skiing, judo, roller skating, vigorous swimming, vigorous long distance bicycling)

b) MODERATE EXERCISE (NOT EXHAUSTING)

(e.g., fast walking, baseball, tennis, easy bicycling, volleyball, badminton, easy swimming, alpine skiing, popular and folk dancing)

c) MILD EXERCISE (MINIMAL EFFORT)

(e.g., yoga, archery, fishing from river bank, bowling, horseshoes, golf, snow-mobiling, easy walking)

Times Per Week

2. During a typical **7-Day period** (a week), in your leisure time, how often do you engage in any regular activity **long enough to work up a sweat** (heart beats rapidly)?

OFTEN	SOMETIMES	NEVER/RARELY
1. 🖓	2. 🖓	3. 🖓

The Shuttle Walking Test (SWT) is an objective, reproducible measure of functional capacity. It was originally designed for use in patients with chronic obstructive pulmonary disorders and has been found to be a reproducible and valid outcome measure (Singh et al, 1992, 1994).

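### Test-retest reliability of the numeric Godin activity score is assigned to kappa with no weights or categories; an unweighted kappa on the raw score would substantially understate it

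*Combined protocol and SAP*

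**What the plan says.** The last paragraph of Section 9.3.3 (Secondary Outcomes and Analyses) sets out a validation of the Godin leisure-time questionnaire against accelerometry. Five statements in the document bear on this point.

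- **Test-retest.** The plan is that "test re-test reliability of the Godin Questionnaire will be assessed using Kappa statistic". This is restricted to a stable subset, namely people whose accelerometer result "did not change between assessment periods (change of less than 10% from baseline"). The form of kappa, the result it applies to and any cut points are not given.
- **Internal consistency.** "Internal consistency of the Godin questionnaire will be assessed using Cronbach alpha and Intraclass Correlation Coefficient". This is the only place where an ICC is named.
- **Validity and responsiveness.** Correlation between the Godin score and active minutes "will be assessed using Pearson or Spearman correlation depending on distribution of the data", and responsiveness is modelled by linear regression with the score as predictor.
- **What the score is.** Section 4.2.3 says that the instrument "uses frequency and intensity of leisure time activity to calculate a total leisure time activity score". Appendix 3.3 adds that "Total weekly leisure activity is calculated in arbitrary units by summing the products of the separate components", with weights 9, 5 and 3 and a worked example totalling 99.
- **A categorical item.** Question 2 in Appendix 3.3 asks "how often do you engage in any regular activity" that raises a sweat, with three ordered answers.

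No reliability threshold, target or sample size is stated for this validation.

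**The concern.** Kappa is a chance-corrected measure of agreement between categories. The Godin total is a count-based numeric score with many possible values, and the plan treats it as numeric for validity and responsiveness, then names a categorical statistic for reliability. In its plain, unweighted form, kappa gives credit only for identical scores. A participant who reports one light session fewer at the second visit counts as fully discordant, just as if the score had fallen to zero. The usual agreement measure for a repeated numeric score is an ICC, which the plan attaches to a different property.

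What is at stake is the published reliability coefficient for the questionnaire in this population. It could be far too low, and a reader could not tell from the plan which coefficient had been intended.

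**Working it through.** **Inputs from the document.** Scoring formula 9S + 5M + 3L (Appendix 3.3); kappa, unspecified (Section 9.3.3); at most 150 participants randomized (Section 9.2). The worked example reproduces: 9×3 + 5×6 + 3×14 = 27 + 30 + 42 = 99. There is no planned reliability figure to reproduce.

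**Inputs assumed, because the document gives none.** True reliability, score distribution and size of the stable subset. Weekly counts were drawn from negative binomial distributions with means (S, M, L) of (0.5, 2, 4), (0.1, 0.7, 2.5) and (0.03, 0.3, 1.2). The mean totals are then:

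- more active: 9×0.5 + 5×2 + 3×4 = 26.5
- low: 9×0.1 + 5×0.7 + 3×2.5 = 11.9
- very low: 9×0.03 + 5×0.3 + 3×1.2 = 5.37

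The latent correlation between the two occasions was 0.80, 0.90 or 0.95; n was 30, 60 or 100; each setting had 400 replicates.

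**Step 1: why exact agreement is too strict.** Change the worked example by one light session: 27 + 30 + 3×13 = 96. Unweighted kappa scores the pair 99 and 96 as a disagreement, exactly as it scores 99 and 0.

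**Step 2: formulas.**

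- Unweighted kappa = (p_o − p_e)/(1 − p_e), where p_o is the proportion of identical scores and p_e the proportion expected by chance.
- Weighted kappa = 1 − (mean observed distance)/(mean distance over all cross-pairs), with distance |a − b| (linear) or (a − b)² (quadratic).
- Absolute-agreement ICC(2,1) = (MSR − MSE)/[MSR + (k − 1)MSE + k(MSC − MSE)/n], with k = 2 occasions and MSR, MSC and MSE the mean squares for participants, occasions and error.

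**Step 3: results at n = 60 (means over replicates).** The three-category columns use assumed cut points of 14 and 24.

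| Activity level | Latent correlation | ICC | Kappa, raw score | Linear-weighted, raw | Quadratic-weighted, raw | Kappa, 3 categories | Quadratic-weighted, 3 categories |
|---|---|---|---|---|---|---|---|
| More active | 0.80 | 0.74 | 0.06 | 0.50 | 0.74 | 0.42 | 0.62 |
| More active | 0.90 | 0.86 | 0.11 | 0.64 | 0.86 | 0.54 | 0.75 |
| More active | 0.95 | 0.92 | 0.18 | 0.73 | 0.92 | 0.65 | 0.83 |
| Low | 0.80 | 0.72 | 0.15 | 0.49 | 0.72 | 0.42 | 0.61 |
| Low | 0.90 | 0.84 | 0.24 | 0.63 | 0.84 | 0.55 | 0.74 |
| Low | 0.95 | 0.91 | 0.34 | 0.73 | 0.91 | 0.66 | 0.82 |
| Very low | 0.80 | 0.69 | 0.27 | 0.50 | 0.69 | 0.39 | 0.52 |
| Very low | 0.90 | 0.81 | 0.37 | 0.63 | 0.81 | 0.51 | 0.65 |
| Very low | 0.95 | 0.89 | 0.49 | 0.73 | 0.89 | 0.65 | 0.76 |

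At n = 30 and n = 100 the ICC and the raw-score kappas stay within 0.02 of these values; the three-category columns move by up to 0.06. As a hand check on row 2, 13% of score pairs were identical; with about 2% expected by chance, (0.13 − 0.02)/(1 − 0.02) = 0.11.

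Unweighted kappa is least low when activity is very low, because small totals leave few distinct scores. Quadratic-weighted kappa on the raw score reproduces the ICC.

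**Step 4: the ICC beside Cronbach alpha.** The average-measures consistency ICC is (MSR − MSE)/MSR, with items in place of occasions. That is algebraically Cronbach alpha. On one simulated three-item data set both equal 0.626. The single-item form is 0.358, and stepping it up to three items returns the same figure: 3×0.358/(1 + 2×0.358) = 1.074/1.716 = 0.626. The second coefficient adds no information and does not distort the first.

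**The case against.** The strongest reply is that the plan never says unweighted and never says raw score. Quadratic weights would give essentially the ICC. Kappa also suits some outputs of this instrument: question 2 has three ordered levels, and the frailty criterion in Appendix 3.5 uses the score as a yes/no cut at the lowest normative quintile. The test-retest sentence refers to the questionnaire, whereas the correlation and regression sentences refer to its score. All of this stands, and it limits the conclusion to a conditional one. It does not remove the gap: if kappa was meant for a categorical result, no test-retest analysis is planned for the total, which is the quantity that the rest of the paragraph validates.

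Three stronger readings are tempting, and the document supports none of them.

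- A reader might infer that a reliable questionnaire would be reported as unreliable. That needs unweighted kappa on raw totals and a threshold for calling an instrument unreliable; the plan fixes neither.
- A reader might infer that internal consistency is also assessed by the wrong statistic. Cronbach alpha is planned there, and the ICC beside it is redundant or loosely labelled.
- A reader might infer damage to the Godin outcome or to frailty status. Nothing in Sections 4.2.3 or 9.3.3 or in Appendix 3.5 makes either depend on the kappa result, and the validation also rests on correlation, internal consistency and responsiveness.

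**Conclusion.** The point holds in conditional form. Kappa is mismatched to a numeric total and under-specified. If it is run unweighted on the raw score, reliability would be substantially understated: about 0.06 to 0.49 where the ICC is about 0.69 to 0.92. Linear weights (0.48 to 0.74 over all settings) and an unweighted three-category split (0.37 to 0.66) also fall below the ICC; quadratic weights on the raw score do not.

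These sizes rest on the assumed distributions, reliabilities, subset sizes and cut points. The direction for unweighted kappa was the same in every setting. The issue is minor: it concerns one coefficient in an ancillary validation and leaves every treatment comparison and the sample size untouched.

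**What to change.** In Section 9.3.3:

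1. For test-retest of the total score, name a two-way, absolute-agreement, single-measurement ICC with its 95% confidence interval, and add limits of agreement in score units.
2. Keep kappa only for question 2 or a categorised activity level, stating the categories and the weights.
3. Keep Cronbach alpha for internal consistency. Drop the ICC there, or state its form and say that the average-measures consistency version equals alpha.
4. Say which pair of visits supplies the retest. Under Section 7.2, "Outcome assessments (as detailed in Section 4.2) will occur at baseline, 12, 26 and 52 weeks", so the shortest gap is 12 weeks and the choice affects how any coefficient is read.

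The cost is a few sentences, submitted for ethics review as Section 10.2 requires for protocol changes. No new data, visits or participants are needed.

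### The planned responsiveness analysis of the Godin questionnaire contains no change term, so it tests cross-sectional agreement and could label a change-blind instrument as responsive

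*Combined protocol and SAP*

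**What the plan says.** The validation of the Godin questionnaire is the last paragraph of Section 9.3.3. It has four parts:

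- **Agreement with accelerometry:** "Correlation between Godin Questionnaire Score and active minutes (light, moderate and moderate-vigorous activity) measured by accelerometry at each study assessment time point", by Pearson or Spearman coefficient.
- **Internal consistency:** Cronbach alpha and intraclass correlation.
- **Test-retest reliability:** assessed in people whose accelerometer minutes "did not change between assessment periods (change of less than 10% from baseline").
- **Responsiveness:** "Responsiveness will be modelled using linear regression with Godin questionnaire score as the primary predictor of active minutes measured by accelerometry". The model may be extended: "Additional predictors including sex, age, diabetes and other comorbidities will be added to the model as sample size will allow".

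The same section sets the significance threshold: "For all analyses, two-sided p < 0.01 will be statistically significant". It gives no separate criterion for calling the questionnaire responsive.

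Section 4.2.3, item 3, makes the questionnaire a change outcome at 12, 26 and 52 weeks, next to accelerometry: "Using the Godin-Shephard Leisure-Time Exercise Questionnaire, which uses frequency and intensity of leisure time activity". Appendix 3.5 uses its score for the low-activity criterion of frailty.

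**The concern.** Responsiveness is the ability of an instrument to register change within a person. The stated model can be fitted to a single visit, where no one has yet changed. Its slope then reflects stable differences between people: those who are generally active score higher. A questionnaire can do that well and still give the same answer, apart from noise, before and after a real change in activity.

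If a significant slope were reported as responsiveness, readers would have unwarranted grounds for taking changes in the Godin score at face value. This matters most where no accelerometer record exists. Under the COVID-19 procedure in Appendix 5, accelerometry stops while the questionnaire continues by phone, email or mail.

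**Working it through.** **1. Reading the text.** The responsiveness sentence and its covariate list contain no change score, baseline value, time term or within-person term. Three comparisons within Section 9.3.3 bear on whether change was simply left unsaid:

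- Where the section means change on change, it says so: "The degree to which change in symptom burden correlates with change in EQVAS will be assessed".
- In the validation paragraph, change is used only to select people who did not change, for test-retest reliability. Those who did change get no analysis.
- The nearest change-based text is "Change in all other secondary outcomes over time will be compared between groups". That compares arms and does not link change in score to change in accelerometer minutes.

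No other section supplies a change-based responsiveness analysis.

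**2. Inputs.** The plan states no figure for this analysis, so there is none to reproduce.

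- n = 150 × (1 − 0.30) = 105, from the target and dropout in Section 9.2.
- Two-sided p < 0.01, borrowed from the general rule in Section 9.3.3.
- Assumed, because the documents are silent: a baseline correlation r of 0.2 to 0.5 between score and minutes; SD of individual change in activity 0.3 or 0.6 of the baseline SD; a mean rise of 0.5 SD in half the participants; minutes measured without error.

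**3. A questionnaire blind to change.** Let baseline activity A0 have SD 1, and follow-up activity be A1 = A0 + D, where D is the change. At both visits the score is r × A0 plus fresh, independent error, scaled to SD 1. It never depends on D.

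**4. Regression as written, at follow-up.** Covariance(score, A1) = r. Variance(A1) = 1 + SD² + 0.5² × 0.25 = 1 + SD² + 0.0625, which is 1.1525 for SD 0.3 and 1.4225 for SD 0.6. The follow-up correlation is therefore r/1.0735 or r/1.1927. By Fisher's z, the chance of p < 0.01 is about Φ(atanh(correlation) × √(n − 3) − 2.576).

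For r = 0.4 and SD 0.3: correlation 0.3726, atanh 0.3914, × √102 = 3.953, and Φ(1.377) = 0.916. For SD 0.6: correlation 0.3354, atanh 0.3489, × √102 = 3.523, and Φ(0.947) = 0.828.

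Simulation with 2,000 runs per setting agrees (n = 105, one follow-up visit; each range runs from SD 0.6 to SD 0.3):

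| Assumed r | Formula | Simulation |
|---|---|---|
| 0.2 | 19-25% | 19-26% |
| 0.3 | 51-63% | 52-63% |
| 0.4 | 83-92% | 83-92% |
| 0.5 | 97-99% | 97-100% |

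With all 150 participants the simulated shares are 29-38%, 71-82%, 97-99% and 100%. Pooling two visits in one ordinary regression, which the plan neither states nor excludes, gives 51-60% at r = 0.2 and 92-95% at r = 0.3 (n = 105).

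**5. Change on change.** The difference between the two scores is pure error and independent of D, so the expected rate is the nominal 1%. Simulation gives 0.7% to 1.4% over every setting and both sample sizes.

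**The case against.** The strongest reply is that the analysis is labelled responsiveness, so the authors probably meant change scores and the sentence is merely short. That may be so. But the text does not say it, and a statistician who follows the text would fit the level model. It can also be said that the regression is not a pure repeat of the correlation, since it adds covariates and is not tied to one visit. That is true, but neither feature brings in change.

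A reader might infer that a change-blind questionnaire is certain, or nearly certain, to be declared responsive. The documents do not support that. They set no criterion for responsiveness, and they give no correlation between score and accelerometer. At r = 0.2 the misleading result appears in roughly a fifth to a quarter of trials. Fewer usable files lower it further: with an assumed 60 valid records and a follow-up correlation of 0.2, 0.3 or 0.45, Fisher's z gives about 15%, 41% and 86%.

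A reader might also infer that the trial's findings on activity or frailty would fall with it. They would not. Arms are compared on change whatever the responsiveness result; activity is also measured by accelerometry; the score feeds one of five frailty criteria, of which three are needed; and validating the questionnaire is not among the objectives in the synopsis or Section 3.

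**Conclusion.** The point holds as a method that does not match its label. The model in Section 9.3.3 tests whether score and activity agree across people, and a significant result would say nothing about responsiveness. The chance of a misleading result is modest if the cross-sectional correlation is near 0.2, and high (83% or more at n = 105) if it is 0.4 or above. Those figures rest on the borrowed 0.01 threshold, a single follow-up visit and the assumed correlations and change distributions above. The conclusion about the model itself rests on none of them. The consequence is confined to a secondary measurement-validation claim, so this is a low-priority correction.

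**What to change.** In Section 9.3.3, define responsiveness as the regression of within-person change in active minutes on within-person change in Godin score, from baseline to 12 weeks and likewise to 26 and 52 weeks. Include participants with valid accelerometer files at both visits. Report the slope and the correlation with confidence intervals, and state how they will be judged. Keep the level-on-level model, labelled concurrent validity.

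The change is to the analysis text only, since both measures are already scheduled at baseline and every follow-up visit. The cost is fewer usable pairs: each file must meet the rule in Section 4.2.3 (at least 3 days with 8 hours of wear), and accelerometry was suspended for visits under the COVID-19 procedure in Appendix 5. The number of pairs at each interval should be reported. Active minutes can stay as defined in Section 4.2.3. Removing minutes spent in dialysis sessions would need session clock times, which the data lists in Section 7.1 do not include.
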